10.5 Handling of Multiplicity

The overall type I error rate of the primary and the ranked secondary endpoints will be strongly controlled using the approach of fixed-sequence multiple testing procedure.¹ Specifically, the testing will utilize the endpoint sequence of the primary and ranked secondary endpoints in the order as specified in Section 10.2 and Section 10.3 at the pre-specified alpha level. That is, only if success has been demonstrated for the primary endpoint of clinical remission will the testing continue to the first ranked secondary endpoint of endoscopic improvement. If success has been demonstrated for the first ranked secondary endpoint, then testing will continue to the next ranked secondary endpoint. Similarly, testing will continue through the other ranked secondary endpoints only if success was met for the preceding endpoint; otherwise, statistical testing will stop.

No multiplicity adjustment will be applied to the additional efficacy endpoints listed in Section 10.4. The analysis for additional efficacy endpoints will be performed at the nominal α level of 0.05 (two-sided).

10.6 Efficacy Subgroup Analysis

The subgroups listed below will be used in subgroup analyses of the primary endpoint of the Maintenance Study.

- Sex (male, female)
- Age (\leq median, $>$ median)
- Race (white, non-white)
- Baseline corticosteroid use (yes, no)

- Baseline immunosuppressant use (yes, no)
- Baseline Mayo Score (≤ 9 , > 9)
- Baseline Mayo Score (\leq median, $>$ median)
- Prior exposure to anti-TNF (yes, no)
- Baseline weight (\leq median, $>$ median)
- Presence of pancolitis at Baseline (yes, no)
- Disease duration at Baseline (\leq median, $>$ median)
- Baseline hs-CRP (≤ 5 mg/L and > 5 mg/L)
- Baseline hs-CRP (\leq median, $>$ median)
- Baseline albumin (\leq median, $>$ median)
- Region (US versus non-US)

11.0 Safety Analysis

11.1 General Considerations

All safety analyses will be performed on the integrated safety analysis set and the Japan safety analysis set for the Maintenance Study. The safety variables will be summarized by treatment regimen according to the treatment a subject actually received. Treatment group differences between the adalimumab 40 mg eow treatment group and the adalimumab 40 mg ew treatment group in safety parameters will be evaluated using two-sided tests at the significance level of 0.05.

Unless otherwise specified, the treatment group differences in continuous safety variables (e.g., change from baseline to final observation on laboratory tests) will be assessed using an ANOVA model with the term of treatment, and the treatment group differences in categorical safety variables will be evaluated using a Fisher's exact test.

11.2 Analysis of Adverse Events

11.2.1 Treatment-Emergent Adverse Events

Treatment-emergent AEs during the Maintenance Study are defined as events that begin or worsen either on or after the first dose of the study drug in the Maintenance Study and within 70 days after the last dose of the study drug.

An overview of treatment-emergent AEs, including AEs of special interest such as adverse events leading to death and adverse events leading to premature discontinuation, AEs by Medical Dictionary for Drug Regulatory Activities (MedDRA version 21.0 or later) preferred term and system organ class, AEs by maximum relationship to study drug, and AEs by maximum severity will be summarized by number and percentage. In addition, an overview of treatment-emergent AEs will be summarized by onset of adverse events in 3-month interval for the integrated safety analysis set.

The number and percentage of subjects experiencing treatment-emergent adverse events will be summarized for the following adverse event categories.

- Any treatment-emergent adverse event.
- Any treatment-emergent adverse event that was rated with reasonable possibility of relationship to study drug by the investigator (Reasonable Possibility).
- Any treatment-emergent severe adverse event.
- Any treatment-emergent serious adverse event.
- Any treatment-emergent adverse event leading to discontinuation of study drug.
- Any treatment-emergent adverse event leading to death.
- Any treatment-emergent adverse event of special interest.
- Any deaths.

Treatment-emergent adverse events will be summarized as follows:

- Grouped by System Organ Class and Preferred Term.
- A by-subject listing will be provided.
- Grouped by System Organ Class, Preferred Term and Severity.
- Grouped by System Organ Class, Preferred Term and Relationship to Study Drug.
- Grouped by System Organ Class, Preferred Term and onset of adverse events in 3-month interval (for the integrated safety analysis set).
- Grouped by System Organ Class and Preferred Term with subject numbers.

In treatment-emergent AE tables, a subject who reports more than one treatment-emergent AE in different system organ classes will be counted only once in the overall total. A subject who reports two or more different preferred terms which are in the same SOC will be counted only once in the SOC total. A subject who reports more than one treatment AE with the same preferred term will be counted only once for that preferred term using the most extreme incident (i.e., most "severe" for the severity tables and most "related" for the relationship tables).

Adverse events will also be summarized by maximum severity. If a subject has an adverse event with unknown severity, then the subject will be counted in the severity category of "unknown," even if the subject has another occurrence of the same adverse event with a severity present. The only exception is if the subject has another occurrence of the same adverse event with the most extreme severity – "Severe." In this case, the subject will be counted under the "Severe" category.

Adverse events will also be summarized by maximum relationship to study drug, as assessed by the investigator. If a subject has an adverse event with unknown relationship, then the subject will be counted in the relationship category of "unknown," even if the subject has another occurrence of the same adverse event with a relationship present. The only exception is if the subject has another occurrence of the same adverse event with a relationship assessment of "Reasonable Possibility." In this case, the subject will be counted under the "Reasonable Possibility" category respectively.

Incidence rates per 100 patient years of exposure to study drug will be presented for AE overviews and for AEs by SOC and preferred term where the number of events will be used as the numerator.

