4.2 Design Diagram

This is a Phase 3, double-blind, randomized, multicenter study of higher versus standard adalimumab dosing regimens for induction and maintenance therapy in subjects with moderately to severely active UC (Mayo Score of 6 to 12 points with an endoscopy subscore of 2 or 3, confirmed by a central reader). For all Mayo Score evaluations throughout the study, the stool frequency and the rectal bleeding subscores will be calculated based on entries recorded in daily electronic patient diaries.

The Japan Sub-Study was designed to enroll 100 Japanese subjects (60 subjects in the higher induction dose regimen and 40 subjects in the standard induction dose regimen) at approximately 21 sites in Japan to meet scientific and regulatory objectives without enrolling an undue number of subjects in alignment with ethical considerations. There are also 840 subjects in a Main Study to be enrolled at 125 sites worldwide outside Japan.

[figure not shown]
This study will include:

- An up to 21 days Screening Period
- An 8-Week Double-Blind Induction Study
- A 44-Week Double-Blind Maintenance Study
- A 70-Day Follow-Up Period

During both the Induction Study and the Maintenance Study, visit week designations will represent weeks since first adalimumab dose in the Induction Study. Week 0 (Baseline) will reflect the date of first adalimumab dosing in the Induction Study. Week 8 will represent the final assessment in the Induction Study and the beginning of the Maintenance Study. Week 52 will represent the final assessment in the Maintenance Study (representing 44 weeks of maintenance treatment in the Maintenance Study). A subject's participation in the study is anticipated to be up to 65 weeks. There is a \pm 3 day window for all study visits. An effort will be made to bring subjects back to their original scheduled visit (calculated from Baseline) if they are out of the visit window.

A schematic of the study design is presented in [Figure 1](#).

Figure 1. Study Schematic (Japan Sub-Study)

8-Week Double-Blind Induction Study

[figure not shown]
Subjects who met all of the inclusion criteria and none of the exclusion criteria were to be enrolled into the 8-Week Induction Study. The Main Study and the Japan Sub-Study would each allow enrollment of up to 25% of subjects with previous infliximab exposure.

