Subjects were to be randomized via interactive response system (IRT) at Baseline (Week 0) to one of 2 double-blinded adalimumab induction regimens (higher dose or standard dose) in a 3:2 ratio. Use of the 3:2 randomization scheme allows for collection of additional safety data with the higher induction dose regimen. The randomization was to be stratified by:

- Previous infliximab use, and
- Baseline corticosteroid use.

The higher induction dose regimen of 160 mg at Weeks 0, 1, 2, and 3, followed by 40 mg at Weeks 4 and 6 leads to a total adalimumab dose over 8 weeks that is approximately twice that of the standard induction regimen (720 mg versus 320 mg) as shown in Figure 2 below.

Figure 2. 8-Week Double-Blind Induction Study

Subjects would return to the study site at scheduled visits and complete study procedures for each visit.

At Week 4, all subjects who were on oral corticosteroids at Baseline would have their corticosteroid dose tapered according to the proposed tapering schedule outlined in the protocol. If the Investigator felt that the steroid taper was not advisable for a particular subject at Week 4, the SDP should have been consulted for evaluation and approval.

44-Week Double-Blind Maintenance Study

The TDM regimen in the maintenance period will not be applied to the Japan Sub-Study because of logistical challenges in obtaining adalimumab serum concentration results

within the time period specified in the Main Study. At the conclusion of the 8-Week Double-Blind Induction Japan Sub-Study, subjects will return to the study site and will be re-randomized via IRT into the 44-Week Double-Blind Maintenance Japan Sub-Study to one of two treatment groups in a 1:1 ratio:

- Adalimumab 40 mg eow.
- Adalimumab 40 mg every week (ew).

Subjects in the adalimumab 40 mg eow treatment group will continue to receive 40 mg eow until the end of the study. Subjects in the adalimumab 40 mg ew treatment group will start 40 mg ew at Week 8 until the end of the study.

70-Day Follow-Up/Premature Discontinuation

Subjects may discontinue adalimumab treatment at any time during study participation. Subjects who end study participation early will have a premature discontinuation (PD) Visit. Subjects will have a follow-up phone call approximately 70 days after the last administration of study drug to obtain information on any new or ongoing AEs. The 70 day follow-up phone call will not be required for any subject who initiates commercial adalimumab.

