9.0 Study Drug Exposure and Compliance

Study drug exposure and compliance will be summarized using the mean, standard deviation, minimum, median, and maximum. Exposure to study drug (total patient-years) will be summarized by treatment group for the Maintenance Study.

The number of injections received at each schedule time point will be summarized with frequencies and percentages for each treatment group for the Maintenance Study.

Study Drug Exposure (in Days) during the Maintenance Study

Study drug exposure is calculated as:

- Date of last dose of Maintenance Study drug – Date of first dose of Maintenance Study drug + 14 days

Study Drug Compliance:

Treatment compliance will be summarized for each treatment group in the I-ITT and J-ITT populations. The treatment compliance is defined as the number of injections actually taken by the subject divided by the number of injections planned to be taken by the subject during the Maintenance Study.

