For all-cause and UC-related hospitalization and surgery rates during Weeks 8 – 52, adjusted incidence rates will be used to compare the risk between the treatment groups. Adjusted rates will be calculated as the number of subjects with the respective event divided by the time at risk. For subjects with an event during the study period, time at risk is the patient-years (PYs) from Week 8 to the first event. For subjects without an event during the study period, time at risk is PYs from Week 8 to the end of study follow up period. Relative risk ratios of the incidence rates and confidence intervals will be

calculated to evaluate the statistical significance of the difference between treatment groups using z-score normal approximations. Additionally, because subjects could have more than one hospitalization during the follow-up period, an event-based approach will be taken. The total number of hospitalizations during the Weeks 8 – 52 will be compared between the treatment groups using Poisson regression with the length of follow-up as the offset variable. Multiple events will be counted in this model.

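### Maintenance AE rates count events to 70 days after the last dose but divide by exposure that stops at 14 days, leaving up to 56 days per subject with no person-time

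*SAP*

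**What the plan says.** All of the following is in the Maintenance SAP.

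- **Events counted (Section 11.2.1).** A treatment-emergent AE begins or worsens on or after the first maintenance dose and "within 70 days after the last dose of the study drug".
- **Rate (Section 11.2.1).** "Incidence rates per 100 patient years of exposure to study drug will be presented for AE overviews", and also by SOC and preferred term, "where the number of events will be used as the numerator".
- **Exposure (Section 9.0).** Exposure in days is the date of the last maintenance dose minus the first, plus 14 days. The second half of that formula reads "Date of first dose of Maintenance Study drug + 14 days"; the 14 days are added to the last-minus-first difference. The same section totals this quantity in patient-years. No other person-time is defined for AE rates.
- **Follow-up (Section 4.2).** The design includes "A 70-Day Follow-Up Period", ending in a phone call about AEs. There is an exception: "The 70 day follow-up phone call will not be required for any subject who initiates commercial adalimumab".
- **Hospitalisation and surgery (Section 10.4).** For subjects without an event, "time at risk is PYs from Week 8 to the end of study follow up period". Repeat admissions are counted in a Poisson regression, "because subjects could have more than one hospitalization during the follow-up period", and the total compared is the one for Weeks 8–52.

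**The concern.** A rate per 100 patient-years is interpretable when an event can be counted only during time that enters the denominator. Here the numerator runs 56 days longer than the denominator. The SAP states each window separately but nowhere notes that the rate combines two different ones.

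The absolute rates are at stake. They are planned for the AE overviews and for every SOC and preferred term, on both the integrated and the Japan safety sets (Section 11.1). The excess depends on how early subjects stop and on how much of the 70 days is observed, and neither is visible in a rate table. Two analysis sets with the same underlying risk but different dropout, or different uptake of commercial adalimumab, would show different rates.

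Two smaller points sit in Section 10.4. The end of follow-up that closes time at risk for event-free subjects is not defined. The Poisson regression counts several admissions per subject but names no robust variance or overdispersion term.

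**Working it through.** The SAP states no AE rate or person-time total, so there is no figure to reproduce. What can be checked is how the two windows compare.

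**Inputs from the SAP:** AE window to last dose + 70 days (Section 11.2.1); exposure to last dose + 14 days (Section 9.0); 44 weeks = 308 days of maintenance (Section 4.2).

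**Assumptions (not in the SAP):** day of last dose, early-stopping proportions, event rate after exposure ends, and share of the late window observed.

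**Formulas.** With the last dose on Rx Day L:

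- exposure = (L − 1) + 14 = L + 13 days
- AE window = (L − 1) + 70 = L + 69 days
- gap = 56 days
- excess over the rate within the exposure window = k × 56/(L + 13)

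Here k = f × c, where f is the event rate after exposure relative to that during exposure, and c is the share of the 56 days observed.

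**Per subject**

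| Assumed last dose | Exposure (days) | AE window (days) | k=1 | k=0.75 | k=0.5 | k=0.25 | k=0 |
|---|---|---|---|---|---|---|---|
| Day 295 (Week 50) | 308 | 364 | 18.2% | 13.6% | 9.1% | 4.5% | 0% |
| Day 302 (Week 51) | 315 | 371 | 17.8% | 13.3% | 8.9% | 4.4% | 0% |
| Day 309 (Week 52) | 322 | 378 | 17.4% | 13.0% | 8.7% | 4.3% | 0% |

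For early stoppers, Day 85 gives 56/98 = 57.1% at k=1 and 28.6% at k=0.5. Day 169 gives 56/182 = 30.8% and 15.4%.

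**Pooled arm.** Stoppers at Day 85, completers at Day 295:

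- 20% stopping: mean exposure 0.2 × 98 + 0.8 × 308 = 266 days; excess 56/266 = 21% at k=1
- 40% stopping: mean exposure 0.4 × 98 + 0.6 × 308 = 224 days; excess 56/224 = 25% at k=1

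**Between arms, equal true risk.** In this example the spurious ratio is 1.25/1.21 = 1.03. Letting stoppers leave at Day 29, 85 or 169 and completers take their last dose on Day 295 or 309, 40% versus 20% stopping gives 1.016–1.048 at k=1 and 1.009–1.026 at k=0.5. If completers' capture differs by arm (75% versus 50%, constant rate), the ratio is 1.136/1.091 = 1.04.

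**Hospitalisation.** If follow-up ends at Week 52, the windows match. If it means the 70-day period, an event-free completer contributes 364–378 days against a 308-day event window, a factor of 308/364 = 0.846 to 308/378 = 0.815. The double use of the follow-up term in Section 10.4, next to a count limited to Weeks 8–52, favours the first reading.

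**Poisson model.** The SAP gives no figure for clustering of admissions, so no size can be computed.

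**The case against.** The strongest reply is that this is a recognisable exposure-based convention. Both windows are written down, the rate is named as one per exposure, and a footnote would tell the reader what was divided by what. The between-arm comparison, which is the question of the trial, barely moves. The main AE summaries are numbers and percentages of subjects, which do not change. No test of the rates is specified, and the Fisher tests and the primary and ranked efficacy endpoints are untouched. All of that stands, and it limits the importance of the point. It does not make the absolute rates right.

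A second reply is that extending person-time to 70 days has its own cost. If the event rate halves after exposure ends (Day 295, full observation), the planned rate is 336/308 = 9.1% above the on-exposure rate, while the extended version is 336/364, or 7.7% below it. If no late events occur, the planned rate is exact and the extended one is 308/364, or 15.4% below. The arithmetic is correct, but the extended version estimates something else: the rate over the SAP's own treatment-emergent window, for which its numerator and denominator agree. Against that rate, the planned one is too high by c × 56/(L + 13) whatever f is. A sponsor who wants the on-exposure rate can restrict the events to last dose + 14 days, accepting that the rate table then omits some events that the percentage tables count.

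Third, linking the rate to Section 9.0 is an inference, since Section 11.2.1 gives no cross-reference. The wording matches, however, and no other definition exists.

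**Conclusion.** The concern holds. Followed as written, the Maintenance SAP divides events from a window ending at last dose + 70 days by person-time ending at last dose + 14 days.

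For completers the upper case is an excess of 17–18%, which requires a constant event rate and full 70-day observation. The waiver of the call for subjects who start commercial adalimumab makes full observation less certain for them. The excess shrinks in proportion to k and vanishes if nothing is captured late. These sizes rest on assumed last-dose days, stopping proportions, late event rates and capture. The 56-day gap itself does not.

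This is worth correcting because it affects reported absolute safety rates, but it does not threaten the trial's inferential conclusions. The undefined end of follow-up for hospitalisation needs only clarification. For the Poisson regression, p-values would be too small if admissions cluster within subjects.

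**What to change.** **AE rates (Section 11.2.1).** Choose one:

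- use person-time from the first maintenance dose to the earlier of last dose + 70 days and last contact, with the treatment-emergent definition unchanged; or
- keep exposure as the denominator and count only events up to last dose + 14 days.

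The rate as now planned may stay as a supplementary line, labelled with its two windows.

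**Hospitalisation and surgery (Section 10.4).** State that time at risk for subjects without an event, and the follow-up length in the Poisson offset, both end at the earlier of Week 52 and last contact. Keep the stop at first event for subjects with an event in the first-event rate. For the repeat-admission count, use a robust (sandwich) variance or a negative binomial model.

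**Cost.** SAP wording and minor programming, with no new data. The main AE rates will differ from the exposure-based convention, which the labelled supplementary line covers.

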11.2.2 Adverse Events of Special Interest

The following AEs of special interest will be summarized by number and percentage of subjects experiencing an AE of interest. The AEs of special interest will be summarized and presented using primary MedDRA system organ classes (SOCs) and preferred terms (PTs) for the following AE categories:

- Any Infections AE
- Any Serious Infection AE
- Any Legionella Infection AE
- Any Diverticulitis AE
- Any Opportunistic Infection AE (Excluding Oral Candidiasis and TB)
- Any Oral Candidiasis
- Any Tuberculosis AE
- Any Active Tuberculosis
- Any Latent Tuberculosis
- Any Parasitic Infection AE
- Any Reactivation of Hepatitis B
- Any Progressive Multifocal Leukoencephalopathy (PML) AE
- Any Malignancy AE
- Any Lymphoma AE
- Any Hepatosplenic T-Cell Lymphoma AE (HSTCL)
- Any Non-Melanoma Skin Cancer (NMSC) AE
- Any Melanoma AE
- Any Leukemia AE
- Any Other Malignant AE (Excluding NMSC, Melanoma, Lymphoma, HSTCL, and Leukemia)

- Any Allergic Reaction (Including Angioedema/Anaphylaxis)
- Any Lupus-Like Reactions and Systemic Lupus Erythematosus
- Any Vasculitis AE
- Any Cutaneous Vasculitis AE
- Any Non-Cutaneous Vasculitis AE
- Any Sarcoidosis AE
- Any Autoimmune Hepatitis AE
- Any Myocardial Infarction Related AE
- Any Cerebrovascular Accident Related AE
- Any Congestive Heart Failure Related AE
- Any Pulmonary Embolism Related AE
- Any Interstitial Lung Disease AE
- Any Intestinal Perforation AE
- Any Pancreatitis AE
- Any Stevens-Johnson Syndrome AE
- Any Erythema Multiforme Related AE
- Any Worsening/New Onset of Psoriasis
- Any Demyelinating Disorder
- Any Amyotrophic Lateral Sclerosis AE
- Any Reversible Posterior Leukoencephalopathy Syndrome (RPLS) AE
- Any Hematologic Disorders AE (Including Pancytopenia)
- Any Liver Failure and Other Liver Event AE
- Any Humira Administration Related Medication Errors AE
- Any Injection Site Reaction AE
- Any AE Leading to Death
- Any AE Leading to Discontinuation of Study Drug
- Any Deaths

Additional AEs may be considered for tabulation/summary based on recommendations from Clinical and Safety as deemed appropriate.

